APPENDIX 2: LAB VISIT WINDOWING

Visit	Visit Day	Window of Days	
		non-lab domains	CBC Labs
Baseline	1	<=1	
Day 15	15	n/a	2-18
Day 21	21	n/a	19-25
Day 28	28	n/a	26-45
Month 1	30	2-45	n/a
Month 2	60	46-75	
Month 3	90	76-135	
Month 6	180	136-225	
Month 9	270	226-315	
Month 12	360	316-405	
Month 15	450	406-495	
Month 18	540	496-585	
Month 21	630	586-675	
Month 24	720	676-765	
Month 27	810	766-XX	

If multiple records are assigned per analysis visit, the latest record will be selected for reporting.

An alternate presentation of lab data will display by Cycle. Cycle x is defined as any lab record between Cycle x start date until Cycle $x+1$ start date.

PFIZER CONFIDENTIAL

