2. Follow up through End of Study: Enter data at SOC visits where each subsequent (post palbociclib treatment) MBC treatment regimen is prescribed and at end of study.
3. Breast cancer treatment: including surgery, radiation, systemic chemotherapy, hormone therapy, and/or targeted therapy, in both neoadjuvant/adjuvant and metastatic disease settings, prior to, during, and post palbociclib treatment; supportive care is also collected in the metastatic setting while on this study.
4. Physician MBC Treatment Selection Survey: Treating physicians will complete a treating physician MBC treatment selection survey that will capture the reason(s) for treatment choice at start of palbociclib therapy and at start of subsequent therapies.
5. Clinical assessments: overall clinical response as judged by treating physician, at intervals per standard of care schedule: imaging assessment, clinical progression, and clinical biomarkers.

CCI

7. CBC: Baseline and during palbociclib treatment, enter any CBC during the 1st 3 cycles, then enter Day 1 (or prior to start of a new cycle) CBC for the subsequent cycles as per standard of care.

8. AE/SAE reporting begins at the time of the patient's first dose of palbociclib or the time of the patient's informed consent if s/he is already exposed to palbociclib and up to 28 calendar days following the last administration of palbociclib.

Table 2: EORTC QLQ-C30 and Geriatric Assessments

Data Collection and Entry	Baseline	Through End of Treatment with Palbociclib
	► SOC Visit 1	
EORTC QLQ-C30 ¹	x ¹	x ¹
G8 Screening Tool ²	x ²	x ²
ADL: Activities of Daily Living ²	x ²	x ²

ADL = Activities of Daily Living; EORTC QLQ-C30 = European Organisation for the Research and Treatment of Cancer Quality of Life Questionnaire Core 30

1. EORTC QLQ-C30 will be collected at baseline (before starting palbociclib) then monthly for the first 3 months of treatment with palbociclib, then every three months until the end of treatment with palbociclib.

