Participation in this study is not intended to change the routine treatment patients receive, as determined by their prescribing physicians; all treatment decisions, type, and timing of disease monitoring are at the discretion of the treating physician and patient. Assessments include patient questionnaires and quality of life (EORTC QLQ-C30, G8 Screening Tool,

PFIZER CONFIDENTIAL

Activities of Daily Living [ADL] Questionnaire), site questionnaires, physician metastatic breast cancer (MBC) treatment selection survey, and **CCI** [REDACTED].

Baseline (or Visit 1) is defined as the date of study enrolment when informed consent is obtained and inclusion/exclusion criteria assessed. The Data Entry Schedule is included in Table 1 and the EORTC QLQ-C30 and Geriatric Assessments in Table 2.

Table 1: Data Entry Schedule

Data Collection and Entry ¹	►	Baseline	During Treatment with Palbociclib	Post Treatment with Palbociclib
		SOC Visit 1	SOC Visit 2 through End of Treatment with Palbociclib	Follow-up through End of Study ²
Informed Consent & Inclusion/Exclusion Criteria		x		
Patient Demographics, Study Site Characteristics, Medical History, Baseline Concomitant Medications, Baseline Metastatic Disease Status		x		
Breast Cancer Diagnosis and Recurrence History		x		
Breast Cancer Treatment ³		x ³	x ³	x ³
Physician MBC Treatment Selection Survey ⁴		x ⁴	x ⁴	x ⁴
Performance Status (ECOG)		x	x	
Clinical Assessments ⁵		x ⁵	x ⁵	x ⁵
CCI				
Laboratory: CBC ⁷		x ⁷	x ⁷	
Adverse Events and Serious Adverse Events ⁸		x ⁸	x ⁸	

SOC = Standard of care; ABC = advanced breast cancer; CBC = complete blood count; ECOG = Eastern Cooperative Oncology Group; MBC = metastatic breast cancer; SAE = serious adverse event

1. Data is collected in accordance with normal standard of care visits, enter all data available per Data Entry Schedule into the electronic data capture system.

2. Follow up through End of Study: Enter data at SOC visits where each subsequent (post palbociclib treatment) MBC treatment regimen is prescribed and at end of study.

3. Breast cancer treatment: including surgery, radiation, systemic chemotherapy, hormone therapy, and/or targeted therapy, in both neoadjuvant/adjuvant and metastatic disease settings, prior to, during, and post palbociclib treatment; supportive care is also collected in the metastatic setting while on this study.

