4. Physician MBC Treatment Selection Survey: Treating physicians will complete a treating physician MBC treatment selection survey that will capture the reason(s) for treatment choice at start of palbociclib therapy and at start of subsequent therapies.

5. Clinical assessments: overall clinical response as judged by treating physician, at intervals per standard of care schedule: imaging assessment, clinical progression, and clinical biomarkers.

CCI

7. CBC: Baseline and during palbociclib treatment, enter any CBC during the 1st 3 cycles, then enter Day 1 (or prior to start of a new cycle) CBC for the subsequent cycles as per standard of care.

8. AE/SAE reporting begins at the time of the patient's first dose of palbociclib or the time of the patient's informed consent if s/he is already exposed to palbociclib and up to 28 calendar days following the last administration of palbociclib.

Table 2: EORTC QLQ-C30 and Geriatric Assessments

Data Collection and Entry	Baseline	Through End of Treatment with Palbociclib
	SOC Visit 1	
EORTC QLQ-C30 ¹	x ¹	x ¹
G8 Screening Tool ²	x ²	x ²
ADL: Activities of Daily Living ²	x ²	x ²

ADL = Activities of Daily Living; EORTC QLQ-C30 = European Organisation for the Research and Treatment of Cancer Quality of Life Questionnaire Core 30

1. EORTC QLQ-C30 will be collected at baseline (before starting palbociclib) then monthly for the first 3 months of treatment with palbociclib, then every three months until the end of treatment with palbociclib.

2. G8 Screening Tool and Activities of Daily Living to be completed only for patients equal to or greater than 70 years of age at the time of study enrollment. G8 and ADL will be collected at baseline (before starting palbociclib) then monthly for the first 3 months of treatment with palbociclib, then every three months until the end of treatment with palbociclib. ADL to be completed by the patient or in conjunction with the appropriately delegated site staff, G8 to be completed by the treating physician or the appropriately delegated site staff.

PFIZER CONFIDENTIAL

STUDY OBJECTIVES

The objectives of this prospective NIS of palbociclib in ABC treatment are:

- Palbociclib prescribing and treatment patterns in routine clinical practice in ABC treatment;
- Clinical outcomes;
- MBC treatment sequence prior to, during, and after palbociclib ;

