APPENDIX 1: DERIVED DATA DETAILS

Study End Date: the earliest of study withdrawal date or last contact visit date

Study Duration: defined in days as study end date minus baseline date +1.

Study Day: post-baseline visit or event date minus baseline date +1. For pre-baseline visits or events, study day is defined as pre-baseline visit or event date minus baseline date. Note there is no study equal to 0.

Age at baseline: defined in years as baseline date minus date of birth +1 divided by 365.25.

Duration of disease: defined in days from initial diagnosis date to study enrollment date.

Duration of ABC/MBC disease: defined in days from ABC/MBC diagnosis date to study enrollment date.

Disease-free interval: time from the end of adjuvant/neoadjuvant treatment to the first disease recurrence.

Paloma-3 disease-free interval: defined in days as the time between first diagnosis of breast cancer and onset of metastatic disease or disease recurrence.

Treatment-free interval: defined in days as the time from last dose of prior chemotherapy to first MBC therapy or first study dose whichever occurred earlier.

Line of Therapy (LOT):

Clinical outcome endpoints will be summarized by LOT which is defined based on the number of therapies taken after initial diagnoses of ABC or MBC, but before palbociclib treatment start:

- 1st line: patients had no LOT in the ABC/MBC setting before palbociclib initiation
- 2nd line: patients had one LOT in the ABC/MBC setting before palbociclib initiation
- 2⁺ line: patients had >1 LOT in the ABC/MBC setting before palbociclib initiation

Best Tumor Response: best overall tumor response recorded from palbociclib treatment start until first documentation of progressive disease. Only response assessments recorded on or before the start date of next subsequent line of treatment will be considered.

Clinical Benefit: a best overall tumor response of complete response or partial response at any time, or stable disease for at least 24 weeks post-study treatment initiation. Only response assessments recorded on or before the start date of next subsequent line of treatment will be considered.

Overall Survival (OS): is defined as time (months) from initiation of the palbociclib combination treatment to date of death, due to any cause.

First Hormonal Therapy After Stage III or IV Diagnosis: the first recorded MBC or adjuvant hormonal therapy after initial diagnosis of stage IIIb or IV MBC or ABC.

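### Reporting the latest blood count in windows that run far past their target day makes Month 3 and later values systematically late, and can put mid-cycle counts under the Day 28 and Month 2 labels

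*SAP*

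**What the plan says.** The table in SAP Appendix 2 gives each visit a target day and a window. The relevant rows read "Day 28 28 n/a 26-45", "Month 2 60 46-75" and "Month 3 90 76-135". The Month 2 and Month 3 rows show a single range, which I read as applying to both the CBC and the non-lab columns. Below the table is the selection rule: "If multiple records are assigned per analysis visit, the latest record will be selected for reporting".

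Several counts per window are to be expected. Footnote 7 of the Data Entry Schedule, in Protocol Section 8.3 and again in the SAP, tells sites to "enter any CBC during the 1st 3 cycles, then enter Day 1 (or prior to start of a new cycle) CBC for the subsequent cycles".

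Days are counted from enrolment. SAP Appendix 1 has "Study Day: post-baseline visit or event date minus baseline date +1", and the SAP study design section has "Baseline (or Visit 1) is defined as the date of study enrolment when informed consent is obtained".

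SAP Section 8.8.2 plans summaries of post-baseline lab values and of change from baseline, together with worst grade or value for each cycle and overall. Appendix 2 adds a by-cycle display as an alternative. SAP Section 8.9.6 lists neutrophil mean and median at a series of months.

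**The concern.** A label such as Month 3 tells the reader roughly when the value was taken. When a window extends much further after its target than before it, taking the latest record pulls the reported value towards the far end. The error then has one direction and does not average out over patients.

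There is a second effect early on, when every count is entered. A patient tested in mid-cycle can contribute a mid-cycle count under a label for which another patient contributes a start-of-cycle count. If counts differ between those two points, the summary partly reflects testing intensity. The SAP treats testing intensity as something that varies, since Section 8.9.6 plans an analysis of lab monitoring patterns.

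**Working it through.** **Rebuilding the windows.** Midpoints between adjacent target days give (30+60)/2 = 45, (60+90)/2 = 75, (90+180)/2 = 135 and (180+270)/2 = 225. These reproduce 46-75, 76-135 and 136-225. The Day 28 CBC window ends at day 45, the Month 1 limit; its own midpoint with Month 2 would be (28+60)/2 = 44. Reach before and after target:

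| Visit | Target | Window | Before | After |
|---|---|---|---|---|
| Day 28 | 28 | 26-45 | 2 | 17 |
| Month 2 | 60 | 46-75 | 14 | 15 |
| Month 3 | 90 | 76-135 | 14 | 45 |

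**Month 3, one CBC every S days, treatment continuing.** S is an assumption; neither document states a cycle length. If the latest count in the window fell on or before day 135 - S, the next one would also be in the window. The latest count therefore lies between day 135 - S + 1 and day 135.

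- S = 28: days 108-135, so 108 - 90 = 18 to 135 - 90 = 45 days late.
- S = 35: days 101-135, so 11 to 45 days late.

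This holds wherever the cycles start relative to enrolment. Extra counts can only move the latest record later.

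Under a nearest rule with S = 28, the two counts around day 90 are 28 days apart, so one is within 14 days, and 14 days either side lies inside the window. With S = 35 the first count in the window falls on days 76-110, so the nearest is at most 110 - 90 = 20 days off.

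**Later windows.** Each closed 90-day window ends 45 days after its target (225 - 180, 315 - 270, and so on to 765 - 720). The latest count is again 18-45 (S = 28) or 11-45 (S = 35) days late.

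**Day 28 and Month 2.** Assume the first dose on the enrolment date, 28-day cycles, and CBCs on cycle days 1 and 15 in cycles 1-3, then day 1 only. Counts fall on days 1, 15, 29, 43, 57, 71, 85 and 113.

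| Visit | Counts in window | Latest | Nearest |
|---|---|---|---|
| Day 28 | 29, 43 | 43: cycle 2 day 15, 15 days late | 29: cycle 2 day 1, 1 day late |
| Month 2 | 57, 71 | 71: cycle 3 day 15, 11 days late | 57: cycle 3 day 1, 3 days early |
| Month 3 | 85, 113 | 113: cycle 5 day 1, 23 days late | 85: cycle 4 day 1, 5 days early |

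The range over other assumptions:

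- Mid-cycle CBCs in cycles 1-2 only: Day 28 is still affected, Month 2 is not. In cycle 1 only: neither is.
- Cycle length S: the mid-cycle counts fall on days S + 15 and 2S + 15. They stay within days 45 and 75 only if S is at most 30.
- A 7-day delay with probability p in each cycle, mid-cycle CBCs in cycles 1-3: the share of mid-cycle values is 1 - p for Day 28 (100%, 75%, 50% at p = 0, 0.25, 0.5) and (1 - p)² for Month 2 (100%, 56%, 25%). A simulation with small date variation agreed. It put the average Month 3 value 22 to 34 days after day 90.

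**Testing the nearest rule.**

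- 35-day cycles, same CBC pattern (days 1, 15, 36, 50, 71, 85, 106): nearest picks day 50 for Month 2 and day 85 for Month 3, both mid-cycle. Latest picks days 71 and 106, both cycle day 1.
- First dose 14 days after enrolment, 28-day cycles: nearest picks days 29, 57 and 85, all mid-cycle. Latest picks days 43, 71 and 127, all cycle day 1.

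**The case against.** The strongest reply is that the documents fix neither a cycle length nor a within-cycle CBC schedule and leave monitoring to the physician, so the mid-cycle effect appears only under certain assumptions. That stands for Day 28 and Month 2. It does not remove the Month 3 result, which needs only regular counts and continuing treatment.

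A reader might infer that Month 3 also comes from the wrong point in the cycle. The documents do not support that. After cycle 3 only start-of-cycle counts are entered, so in the illustrated case the Month 3 value is about one cycle late but still a day 1 count.

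It is also fair that a nearest rule can itself select mid-cycle counts, as the last two examples show. Counting from first dose removes the enrolment lag; delayed cycles remain a limit of any calendar window.

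Finally, the SAP already has cycle-aligned outputs, and Section 8.9.6 defers its details to a separate document without citing Appendix 2. Its monthly means might use all counts in a period. So the link to the neutrophil analysis is possible, not established. The by-cycle display, however, does not correct the by-visit and change-from-baseline tables.

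**Conclusion.** The point holds as a modest but worthwhile correction. With one CBC per cycle at 28-day (35-day) spacing, assumed, and treatment continuing, the Month 3 value is always 18-45 (11-45) days late, against at most 14 (20) days off under a nearest rule. The later closed windows carry the same late shift.

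For Day 28, if mid-cycle CBCs are drawn in cycle 2, and for Month 2, only if they are drawn in cycle 3, the rule can substitute a mid-cycle for a start-of-cycle count. It cannot be said that it always does.

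The exposed outputs are the by-visit and change-from-baseline lab summaries, and possibly the monthly neutrophil figures. Worst-grade and by-cycle summaries are unaffected. A reader might go on to doubt the study's safety grading or clinical outcomes; neither depends on this rule, and the analyses concerned are descriptive.

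**What to change.** In SAP Appendix 2, replace the selection sentence: for post-baseline windows, report the record closest to the target day, taking the earlier if two are equally close; use the latest record for baseline only. That agrees with the baseline definition in the SAP's general methods. For CBC windows, count days from the first palbociclib dose, not from enrolment. This also matters for patients already taking palbociclib at consent, whom the adverse-event footnote of the Data Entry Schedule foresees.

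The cost is a few lines of text and a small programming change. When cycles are delayed, the nearest record may still be a mid-cycle count, so the SAP should add that within-cycle patterns are to be read from the by-cycle display.
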